STUDY PROTOCOL

Principal Investigator: [name]

[contact]

E-mail: [contact]

ClinicalTrials.gov number: NCT03972969

Protocol date: 3/16/2022

1. Aims/Objectives

A meta-analysis indicates that falls are very common in Parkinson's disease (PD), even within a brief period of 3 months, when about half of patients will sustain at least 1 fall (Pickering et al., 2007). Randomized, controlled trials (RCT) have examined the effects of exercise interventions on reducing falls in this population; however, with mixed results. The goal of the proposed research is to evaluate two approaches to implementing an exercise program: 1) an in-person exercise program that demonstrated a significant decline in fall rates over time in a small sample of patients (Sparrow et al., 2016) and 2) a home-based program centered around remote, exercise instruction.

In the proposed RCT, 162 VA patients with PD will be randomly assigned to one of three 3-month interventions: in-person exercise, remotely-delivered exercise, or health education. Fall rates will be compared between each exercise intervention group and the health education group.

2. Background Information

2.1 Clinical Manifestations of Parkinson's Disease

PD is a progressive neurodegenerative disorder, characterized by insidious onset. The first signs become clinically manifested when about 70-80% of the dopamine producing cells of the substantia nigra have degenerated (Booij et al., 2001). The cardinal clinical manifestations of PD include resting tremor, rigidity, bradykinesia, and postural instability/gait disturbance (Olanow et al., 2009). Falls are one of the most serious complications of gait disturbances and postural instability in people with PD. People living in the community with PD fall frequently, with 60% falling annually and two-thirds of these falling recurrently (Latt et al., 2009; Allen et al., 2013; Bloem et al., 2001). These fall rates are double those in the general older population (Bloem et al., 2001), and contribute to inactivity, restrictions in mobility, fear of falling, and greater disability (Allen et al., 2010; Wielinski et al., 2005).

2.2 Medical Management of Parkinson's Disease

The treatment of PD primarily focuses on symptom management (Olanow et al., 2009). While dopaminergic drugs have positive effects on symptoms such as bradykinesia and tremor, these drugs have negligible effects in ameliorating balance deficits and reducing falls in patients with PD (Hall et al., 2013; Curtze et al., 2015). The suboptimal pharmacological management of PD led the Movement Disorder Society Evidence-Based Medicine Panel to recommend exercise as an efficacious adjunct to levodopa and other drugs (Fox et al., 2011).

2.3 The Benefits of Exercise in the Management of Parkinson's Disease

Exercise is a key part of the management of PD because it has been shown to retard the deterioration of motor functions and to prolong functional independence (Mak et al., 2017). A recent RCT in PD showed significant improvements in Unified Parkinson's Disease Rating Scale, motor subscale (UPDRS-III) scores following a progressive resistance training program, as compared to a non-progressive stretching, balance, and strengthening program suggesting the importance of progressively more challenging exercises (Corcos et al., 2013). Also, prior work in the area of exercise in both animal models and humans with PD suggests the importance of goal-based motor skill training to enhance motor learning and motor control (Petzinger et al., 2013; Fisher et al., 2008).

Recent clinical trials have specifically examined the effects of exercise interventions on reducing falls in patients with PD. A tai chi program and a strength training program both resulted in a lower incidence of falls, as compared to a stretching program (Li et al., 2012). A group strengthening and balance training program vs. usual care in PD showed no statistically significant reduction in fall rate (Goodwin et al., 2011). A strength training program and a movement strategy training program both resulted in significantly fewer falls, as compared to a life-skills education program (Morris et al., 2015). A minimally supervised, home-based balance

and strengthening program vs. usual care did not significantly reduce fall rate (Canning et al., 2015). Although these recent studies provide some evidence suggesting that falls are modifiable in PD, results are mixed.

There is limited availability of effective treatment options to reduce falls in PD. In this context, evidence from two meta-analyses (Sherrington et al., 2017; Allen et al., 2011) indicates that highly challenging exercise approaches may lead to better outcomes. We investigated the effects of a theoretically driven, highly challenging balance program on fall rate in a randomized, controlled cross-over trial (Sparrow et al., 2016). Twenty-three patients with PD were randomly assigned to 3 months of active exercises (strengthening, range-of-motion, balance activities) or usual care followed by the reverse. The results showed that the balance program was effective in reducing falls.

3. Rationale and Purpose

Identifying interventions that successfully reduce fall rate is critical to reduce disability, improve quality of life, and potentially increase survival in patients with PD. RCTs have examined the effects of exercise interventions on reducing falls in patients with PD; however, with mixed results. Evidence from two meta-analyses (Sherrington et al., 2017; Allen et al., 2011) indicates that progressive and challenging exercise programs may lead to better outcomes.

Patients with PD often have limited access to exercise programs because of distance from a center providing specialized exercise training or their inherent limited functional mobility. An evidence-based exercise program remotely delivered to the home in these patients has the potential to keep patients exercising over the long term and to reach the majority of patients regardless of geographic location or functional limitations to participating in in-person programs. In this context, approximately 34 to 36% of its enrollees live in rural areas (National Center for Veterans Analysis and Statistics, 2016; West et al., 2010). To the best of our knowledge, this will be the first RCT to compare a remotely-delivered program with an in-person program on reducing fall rate in patients with PD. Both programs incorporate the most salient features from prior work (e.g., theoretically driven, progressive, goal oriented).

4. Relevance to Veterans Health

Parkinson's disease is the second most common neurodegenerative disorder, affecting over 80,000 veterans treated within the VA Healthcare System. Falls are a major problem for many patients. A remotely-delivered home-based exercise program has the potential to be accessed easily and conveniently by large numbers of people with PD. The findings of this study may help VA clinicians provide optimal care for the many veterans with PD at risk of falls.

5. Study Design

We will conduct a three-group RCT with a 3-month intervention period and three assessment points (baseline, 3 months, and 6 months). Patients with PD will be randomly assigned to one of three interventions: in-person exercise, remotely-delivered exercise, and health education. All patients will be asked to complete 3 training sessions per week over the 3-month intervention period.

5.1 In-person Exercise Program

The in-person exercise program is guided by Horak's theoretical balance framework for PD (Horak et al., 2009), which describes several interacting systems contributing to balance control (Sparrow et al., 2016). A range of exercises (i.e., strengthening, range of motion, anticipatory and reactive balance activities, altering sensory input, and gait training) address one or more of the systems of balance control and consist of a progression ranging from less challenging to more challenging.

To reduce the risk of an injury from exercising, exercise sessions are stopped immediately if a

participant has symptoms suggestive of a musculoskeletal injury, significant respiratory symptoms, or any suspected cardiac issues. In addition, participants are instructed to contact research staff if they are hospitalized for any reason. VA electronic medical records are reviewed at least once per month for potential adverse events. Participants are called when they miss sessions for 1 week to determine the reason for missing sessions (e.g., adverse event, vacation, etc.). There is an immediate suspension of participation in the exercise program when specific cardiovascular events (myocardial infarction, angina pectoris, symptomatic arrhythmia either supraventricular or ventricular tachycardia, syncope, stroke/TIA) or new concerning symptoms (significant shortness of breath or chest pain, significant lightheadedness, significant muscle discomfort in either arm during or after exercise) occur.

5.2 Remotely-delivered Exercise Program

We have experience successfully implementing remote home-based exercise programs in 3 separate VA clinical trials in PD. The remotely-delivered home-based program includes a variety of exercises (strengthening, range of motion, anticipatory and reactive balance activities, altering sensory input, and gait training) that have been modified in such a way to ensure safe execution in the home environment. The specific exercises are aimed at addressing one or more of the systems of balance control described by Horak et al. (2009).

At the conclusion of the baseline exam, each exercise will be shown to the participant and then the participant will be asked to perform each exercise. Subsequently, exercise sessions are performed at home over a 3-month period and progressed from less challenging to more challenging over time. In order to conduct this in-home training, we have designed and programmed a system taking advantage of smartphone technology to provide remote instruction.

To reduce the risk of an injury from exercising, participants are instructed in every session to stop exercising if they experience symptoms suggestive of a musculoskeletal injury, significant respiratory symptoms, or any suspected cardiac issues and to call their physician as well as study staff. At enrollment, participants are instructed to contact research staff if they are hospitalized for any reason. VA electronic medical records are reviewed at least once per month for potential adverse events. Participants are called when they miss sessions for 1 week to determine the reason for missing sessions (e.g., adverse event, vacation, etc.). There is an immediate suspension of participation in the exercise program when specific cardiovascular events (myocardial infarction, angina pectoris, symptomatic arrhythmia either supraventricular or ventricular tachycardia, syncope, stroke/TIA) or new concerning symptoms (significant shortness of breath or chest pain, significant lightheadedness, significant muscle discomfort in either arm during or after exercise) occur.

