7.1 Falls Assessment

The rate of falls will be assessed prospectively. The collection of detailed and prospective information about falls follows the recommendations of the Prevention of Falls Network Europe consensus statement (Lamb et al., 2005) and a Cochrane Collaborative review (Gillespie et al., 2012). A fall is defined as an unexpected event in which a participant comes to rest on the ground, floor, or lower level. A near fall is defined as an occasion in which a participant felt that he was going to fall but did not actually do so. Participants will be asked to record falls as they occur on monthly calendars supplied by the investigators. Also, they will be asked to record the circumstances surrounding a fall or near fall (i.e., location, time of day, direction of fall, activity being performed, presence of an environmental trigger, injuries sustained, and medical attention received).

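### Section 5.2's every-session stop-and-call instruction is narrower than its own immediate-suspension list, so suspension of a home participant after a non-admitted TIA, faint or lightheadedness could wait for the VA record review

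*Combined protocol and SAP*

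**What the plan says.** Section 5.2 (Remotely-delivered Exercise Program) sets out these safety measures for the home arm:

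- **Every-session instruction.** Participants are to stop exercising on "symptoms suggestive of a musculoskeletal injury, significant respiratory symptoms, or any suspected cardiac issues and to call their physician as well as study staff".
- **Suspension rule.** "There is an immediate suspension of participation in the exercise program when specific cardiovascular events" occur. The list covers MI, angina and symptomatic arrhythmia, and continues with "syncope, stroke/TIA) or new concerning symptoms (significant shortness of breath or chest pain, significant lightheadedness", ending with significant arm muscle discomfort during or after exercise.
- **Contact outside sessions.** "At enrollment, participants are instructed to contact research staff if they are hospitalized for any reason".
- **Record review.** "VA electronic medical records are reviewed at least once per month for potential adverse events".
- **Staff call.** "Participants are called when they miss sessions for 1 week to determine the reason for missing sessions".

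Section 5.1 (In-person Exercise Program) has the same suspension list, record review and staff call. Its contact instruction is also limited to admission: "In addition, participants are instructed to contact research staff if they are hospitalized for any reason". Section 7.1 (Falls Assessment) adds a possible indirect route: "Participants will be asked to record falls as they occur on monthly calendars supplied by the investigators". The circumstances of falls and near falls are recorded as well.

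**The concern.** A suspension rule can act only on what staff know. In a home session the participant is usually the only observer, so the rule depends on what the participant has been told to report. The reporting instruction and the suspension list stand in the same paragraph and do not match. A participant who follows the stated instruction to the letter could have a TIA or a faint, not think of it as a heart problem, avoid admission, and go on with a home program that includes reactive balance work and gets harder over time. The suspension list itself anticipates symptoms outside a session, since arm discomfort counts during or after exercise, yet the call instruction is tied to stopping exercise. Patient safety is at stake here, not the fall-rate comparison.

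**Working it through.** **Step 1. Suspension list against the every-session instruction (both Section 5.2).**

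| Suspension trigger | Reached by the every-session instruction? |
|---|---|
| MI, angina, symptomatic arrhythmia, chest pain | Yes, as a suspected cardiac issue |
| Significant shortness of breath | Yes, as a respiratory symptom |
| Significant arm muscle discomfort | Reasonably, as musculoskeletal or suspected cardiac |
| Syncope | Not named |
| Stroke/TIA | Not named |
| Significant lightheadedness | Not named |

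The last three enter only if the participant reads them as a suspected cardiac issue, or if a respiratory or musculoskeletal symptom comes with them. The suspension list attaches no such condition.

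**Step 2. Do the other stated routes close the gap?** Take a listed event without admission, in a participant who keeps exercising and does not call unprompted.

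| Route | Why it does not act promptly |
|---|---|
| Contact instruction (5.1, 5.2) | Applies to hospitalization only |
| Staff call (5.1, 5.2) | Needs a week of missed sessions |
| VA record review (5.1, 5.2) | At least monthly; sees only what reaches VA records |
| Fall calendars (7.1) | Monthly; capture the event only if it causes a fall or near fall; no safety review stated |

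The record review is the remaining stated adverse-event check.

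**Step 3. How many sessions could pass?** Section 5 asks for 3 sessions a week over 3 months. Taking 3 months as 13 weeks (assumed), 3 × 13 = 39 sessions are planned per participant.

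- Reviews about a month apart: 3 × 52/12 = 13 sessions, and 13/39 = 33% of the program.
- One review per calendar month, early in one and late in the next (a gap of about 60 days): 3 × 60/7 = 25.7, about 26 sessions, and 26/39 = 67%.
- Event never in VA records and no other route acts: all remaining sessions.

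These are worst cases at full adherence. Lower adherence or more frequent reviews shorten them. The documents give no event rate, so the expected number of affected participants cannot be computed.

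**Step 4. Cost of a wider instruction.** Section 1 gives 162 participants in three arms. With equal allocation (assumed), 162/3 = 54 per arm, so 2 × 54 = 108 are in the exercise arms, with 108 × 39 = 4,212 planned exercise sessions. Assume that 5% to 20% have one unnecessary hold: 0.05 × 108 = 5.4 to 0.20 × 108 = 21.6 holds.

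| Length of hold | Sessions lost per hold | Total lost | Share of 4,212 |
|---|---|---|---|
| 1 week | 3 | 16.2 to 64.8 | 0.4% to 1.5% |
| Rest of program (half of it on average) | 39/2 = 19.5 | 105.3 to 421.2 | 2.5% to 10% |

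The plan states no restart rule, so the length of a hold is not known.

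**The case against.** **The protocol only summarizes what participants are told.** The operative wording would be in the smartphone system and the consent documents, which were not in the text reviewed. This stands as a limit. A reader might infer that home participants are never told to report a stroke or a faint; the documents do not support that. They support only a mismatch between two lists in one paragraph. If the script is already broader, aligning the protocol costs almost nothing.

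**The cardiac phrase may be meant broadly.** The plan itself groups syncope and stroke/TIA under cardiovascular events, so its authors may intend the shorter phrase to include them. That is possible, but the attribution is then left to the participant, and lightheadedness is listed separately as a symptom.

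**Several conditions must coincide.** This also stands: no admission, continued exercise and no voluntary call are all needed, and many participants would call anyway. It is why the point is minor.

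**The in-person arm is different.** A reader might carry the same delay over to Section 5.1. The missing between-session instruction is shared, but participants are asked to attend three times a week and staff can learn of an event at the next session. No pre-session check is stated, yet this contact largely removes the delay. The session counts above therefore apply to the home arm.

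**A monthly review might seem to cap the delay at about 13 sessions.** It does not: the wording sets a minimum frequency, not a maximum gap between reviews.

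**Conclusion.** The point holds as a minor patient-safety gap. As stated in Section 5.2, the every-session instruction does not name three of the plan's own suspension triggers and does not explicitly cover events between sessions, and no other stated route prompts an early report when the participant is not admitted. In that situation, suspension that is meant to be immediate can come about 13 sessions late with reviews a month apart, up to about 26 with calendar-month reviews, or not at all if the event stays outside VA records. These figures assume 39 planned sessions, full adherence, continued exercise and no voluntary call. Frequency is unknown, and the script and consent pages were not seen. A reader might infer that the fall-rate results are compromised; nothing here supports that, because the estimand, the negative binomial analysis and the power calculation are unaffected.

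**What to change.** 1. In Section 5.2, add stroke/TIA symptoms, syncope and new significant lightheadedness to the every-session instruction, and word it to cover the interval as well. For example: *stop, or do not start, and call your physician and study staff if, during exercise or since your last session, you have had any of the following.* Keep the qualifiers new and significant to limit needless holds.
2. Extend the instruction to contact staff from hospitalization to any event on the suspension list. This matters mainly in Section 5.2; use the same sentence in Section 5.1 for consistency.
3. Align the smartphone script and consent text if they do not already say this.

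The cost is a wording change for about 108 participants, with some false-positive holds and extra staff calls. Under the assumed 5% to 20% hold rate, about 0.4% to 1.5% of planned exercise sessions would be lost at one week per hold, and about 2.5% to 10% if holds lasted for the rest of the program. A short restart rule would help keep the loss near the lower range. Eligibility, endpoint, sample size and visits need no change.

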5.3 Health Education Control

The group receiving health education will serve as an attention control. The health education control system provides general information via a smartphone about a variety of health topics, including topics on exercise. Participants will be prompted to complete health education sessions three times weekly. The delivery of the system's content makes use of both the audio and video capabilities (still and video images) of the smartphone technology to enhance the educational value of the presentation. There are opportunities for participant interaction, for example, the ability to request additional information within the content area.

During the first four weeks of the intervention, content on exercise based on the Fitness Counts program developed by the National Parkinson Foundation (Chapters 3 & 4) (Cianci, 2006) will be sequentially presented focusing on the benefits of exercise for people with PD (1 session), the types of exercises important for people with PD (1 session), principles of stretching and strengthening exercises (2 sessions), descriptions of safe stretching and strengthening exercises for people with PD (6 sessions), and strategies to overcome barriers to exercise (2 sessions). Participants will be provided with illustrations of the exercise program with written instructions (from the Fitness Counts booklet) to accompany the auditory content. Subsequently, during each session, participants will select a topic from four content areas: common symptoms, medical

conditions, preventive medicine topics, and tips for healthy living with PD.

6. Study Subject Selection

a. Sample Description

Patients with PD will be identified from the VA Boston Healthcare System (Boston, West Roxbury, and Brockton VA medical centers and their five satellite clinics) and the Bedford VA Medical Center and its four satellite clinics with the use of the Corporate Data Warehouse (CDW). Specifically, this approach will involve searching the CDW to identify patients who are 40 years of age or older with an ICD code for PD and a prescription for a dopaminergic medication. To assess electronic medical records we will use the CAPRI system, which provides one interface into the VISTA systems within VISN 1. Patients with PD typically have an initial Neurology consultation and then are seen in Neurology Clinic every 6 months. A standardized VA note format is utilized which includes HPI, medications, and detailed neurologic examination at each visit. The initial VA Neurology consultation will be reviewed with as many subsequent clinic notes as needed to establish the diagnosis of PD and responsiveness to dopaminergic therapy. The two most recent Neurology Clinic notes will also be reviewed to determine current medication use and functional status. Pharmacy records will also be reviewed to confirm stability of medication dosage. Also, Primary Care provider notes and any hospital discharge summaries from the previous year will be reviewed for evidence of exclusionary conditions.

b. Subject Inclusion Criteria

Patients with PD who meet eligibility criteria will be recruited into this study. Specific inclusion criteria will include a physician diagnosis of idiopathic PD; at least 2 of the 3 cardinal signs of PD (resting tremor, rigidity, bradykinesia); response to dopaminergic medication; and an age of 40 years or older.

c. Subject Exclusion Criteria

Specific exclusion criteria will include a diagnosis of angina pectoris (unless symptomatically resolved post-revascularization); a history of myocardial infarction (MI) within 6 months; and a history of ventricular dysrhythmia requiring current therapy.

7. Data Collection and Management

